6.4.1.4 Implant 1 / Study Day 90 ± 5 Days

Subjects will be evaluated for a second implantation which, if cleared, will occur as soon as possible after the visit on Implant 1 / Study Day 90 ± 5 days.

6.4.1.5 *Implant 2 / Study Day 0*

The day of the second implant will be designated as Implant 2 / Study Day 0.

6.4.1.6 *Implant 2 / Study Day 90 ± 5 days*

Subjects will be evaluated for a third implantation which, if cleared, will occur as soon as possible after the visit on Implant 2 / Study Day 90 ± 5 days.

6.4.1.7 *Implant 3 / Study Day 0*

The day of the third implant will be designated as Implant 3 / Study Day 0.

6.4.1.8 *Implant 3 / Study Day 90 ± 5 days*

Subjects will be evaluated for a fourth implantation which, if cleared, will occur as soon as possible after the visit on Implant 3 / Study Day 90 ± 5 days.

6.4.1.9 *Implant 4 / Study Day 0*

The day of the fourth and final implant will be designated as Implant 4 / Study Day 0.

6.4.1.10 *End of Study (EOS) Visit*

For each patient, active safety and efficacy assessments will be completed 120 days after the patient's final implant.

6.4.1.11 *Follow-up*

Long-term follow-up will begin after the patient's EOS visit, and will continue for the duration of each subject's life, at 6-month intervals during the first 2 years of long-term follow-up and then yearly thereafter. All examinations and treatment during this time will be guided by optimal patient care principles and the decisions of the physicians providing overall health care to each subject.

6.4.2 Assignment of data to study time points

Each data observation will be assigned both a nominal study day and an actual study day.

Type of Study Day	Definition
Actual study day	Calculated as the difference in days between date of collection and date of the first implant and will be used as the x-axis for plots of individual subject data over time.
Nominal study day	Calculated as the difference in days between the date of collection and the date of the most recent implant prior to the date of collection, regardless of the study day to which the observation was assigned at data entry (e.g., from the CRF).

Nominal study day will be Observations that do not fall within a nominal study day window ([see Section 6.4.4](#)) will be labeled as "Unscheduled" and will be listed but not summarized or analyzed. Nominal study day will be used for listings and tables (unless otherwise noted), and for figures of grouped observations over time. See [Section 6.4.1.2](#) for the definition of Baseline observations.

6.4.3 Selection of data in the event of multiple records in a study day window

If multiple non-missing observations exist for a nominal Study Day window, all data will be listed however the last valid observation in that window will be used for summaries and analyses.

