6 GENERAL DATA HANDLING / PRESENTATION CONSIDERATIONS

6.1 Listing, Table, and Figure Formats

- In general, listings, tables, and figures will include all subjects in the Treated Population.
- Listings will be ordered by cancer type, unique subject identifier, study day, visit date, and data collection time, if appropriate.
- Tables and figures will be ordered by cancer type and study day and will include summaries for both cancer types individually as well as for all subjects combined.
- The order of cancer type presentation in listing, tables, and figures will be colorectal, then pancreatic.
- Listings will include subject identification, subject initials, subject age and sex, cancer type, study day, date, and data collection time, as applicable.
- Unscheduled data, such as repeat laboratory tests, will be listed but will not be summarized or analyzed.
- Partial dates will be listed as recorded; i.e., there will be no imputation of partial dates for listings.
- Dates will be presented as ddmmmyy.
- Times will be presented as hh:mm (24-hour clock).
- Laboratory data will be presented in conventional units.
- Missing data will be represented on listings as either a hyphen (“-”) with a corresponding footnote (e.g., “unknown” or “not evaluated”), as “N/A” with the footnote “not applicable,” or another entry with an explanatory footnote, whichever is appropriate.
- Missing descriptive statistics or p-values will be output as a hyphen with an explanatory footnote.
- Each listing, table, and figure will be numbered using a decimal-point system for identifying related listings, tables, and figures.
- Each listing, table, and figure will be titled with the listing / table / figure number and a description of the presentation.
- Column headers will contain the unit of measurement, if applicable.
- In tables, column headers will contain the overall sample size of the group associated with the column. The overall sample size will include subjects with missing values for the data presented in the column. The number of subjects with available data for the column will be shown in the body of the table.
- Footnotes will appear at the bottom of each page of listings and tables.

- All listings, tables, and figures will be presented in the landscape orientation with 1-inch margins on all sides.
- In general, the main body of listings and tables will be 10 pt Times Roman font (or similar).
- Footnotes will be 8 pt Times Roman font (or similar).

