6.4.4 Visit windows definitions

The following visit window definitions will be used:

Implant	Time Window			Comment
	From Day (inclusive)	Assessment Day	To Day (inclusive)	
Pre-implant	-28	< 0	0	Implant 1 Baseline
1	---	0	---	Implant 1 Day 0
	7	14	21	Implant 1 Day 14 (I1 / D14)
	23	30	37	Implant 1 Day 30 (I1 / D30)
	53	60	67	Implant 1 Day 60 (I1 / D60)
	83	90	97	Implant 1 Day 90 (I1 / D90) if before Implant 2 or there is no Implant 2
2	---	0	---	≥ 98 days after Implant 1, Day 0 Implant 2 Day 0 (I2 / D0)
	7	14	21	Implant 2 Day 14 (I2 / D14)
	23	30	37	Implant 2 Day 30 (I2 / D30)
	53	60	67	Implant 2 Day 60 (I2 / D60)
	83	90	97	Implant 2 Day 90 (I2 / D90) if before Implant 3 or there is no Implant 3
3	---	0	---	≥ 98 days after Implant 2, Day 0 Implant 3 Day 0 (I3 / D0)
	7	14	21	Implant 3 Day 14 (I3 / D14)
	23	30	37	Implant 3 Day 30 (I3 / D30)
	53	60	67	Implant 3 Day 60 (I3 / D60)
	83	90	97	Implant 3 Day 90 (I3 / D90) if before Implant 4 or there is no Implant 4
4	---	0	---	≥ 98 days after Implant 3, Day 0 Implant 4 Day 0 (I4 / D0)
	7	14	21	Implant 4 Day 14 (I4 / D14)
	23	30	37	Implant 4 Day 30 (I4 / D30)
	53	60	67	Implant 4 Day 60 (I4 / D60)
	83	90	97	Implant 4 Day 90 (I4 / D90)

Implant	Time Window			Comment
	From Day (inclusive)	Assessment Day	To Day (inclusive)	
	113	120	127	EOS
Any visit which occurs outside the above time windows is considered "unscheduled".				

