11.1.3 Clinical laboratory evaluations

Hematology, coagulation, serum chemistry, serum pregnancy, urinalysis, immunology, immunophenotyping, and all other laboratory parameters including those listed in [Protocol Section 5.6](#) will be analyzed at multiple laboratory sites and will be delivered via hard-copy reports to the central data processing center (VSI). Laboratory test names and units of measurement will be standardized by VSI. For select parameters, study day, collection lab, date and time collected, normal range, observed value, change from baseline in relationship to both first and most recent implant, out-of-range flag, and Common Terminology Criteria for Adverse Events (CTCAE) v3.0 toxicity grade (if applicable) will be listed. Laboratory observations with Grade 3 or higher toxicity and/or reported as an AE will be listed. For all parameters, study day, date collected, observed value, normal range, and out-of-range flag will be output to a spreadsheet. For select parameters, observed values and changes from baseline (in relationship to both first and most recent implant) will be summarized for each time point at which laboratory data were collected. Separate series of tables will show numbers and percentages of subjects by out-of-range flag and by toxicity grade. Shift tables will be provided that show numbers and percentages of subjects with normal ↔ abnormal shifts based on out-of-range flags and/or toxicity grades from baseline (in relationship to both first and most recent implant) to each subsequent time point at which laboratory data are collected.

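### SAP 6.1 and SAP 6.4.2-6.4.3 conflict on repeat laboratory tests inside a visit window, and with no worst-grade rule the laboratory toxicity and shift tables can miss transient Grade 3-4 values

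*SAP*

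**What the plan says.** **Assignment to windows.** SAP 6.4.2 computes the nominal study day from the collection date and the most recent implant, "regardless of the study day to which the observation was assigned at data entry". "Observations that do not fall within a nominal study day window" are labelled unscheduled, and are listed but not summarized. SAP 6.4.4 sets windows of Days 7-21, 23-37, 53-67 and 83-97 after each implant, plus Days 113-127 after the fourth. It closes with the same test by date: "Any visit which occurs outside the above time windows is considered" unscheduled.

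**Several records in one window.** SAP 6.4.3 lists them all, but "the last valid observation in that window will be used for summaries and analyses".

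**Repeat tests.** SAP 6.1 says: "Unscheduled data, such as repeat laboratory tests, will be listed but will not be summarized or analyzed". SAP 6.2 again bars unscheduled data from summaries and analyses.

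**Laboratory tables.** SAP 11.1.3 says: "Separate series of tables will show numbers and percentages of subjects by out-of-range flag and by toxicity grade". Shift tables run from baseline "to each subsequent time point at which laboratory data are collected". Neither has a worst-grade or maximum-grade rule. The same section provides a safeguard: "Laboratory observations with Grade 3 or higher toxicity and/or reported as an AE will be listed" (Listing 16.2.8.4).

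**The concern.** An in-window repeat is unscheduled by its nature under 6.1, but scheduled by its date under 6.4.2. The SAP does not say which rule governs. Two programmers could both follow the plan and produce different toxicity tables.

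The more basic gap is that neither rule is designed to show the highest grade a subject reached. A by-visit snapshot suits means and medians. A toxicity table is normally read as showing how many subjects had a severe abnormality, and this one can leave out a short-lived Grade 3-4 value.

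Change in laboratory parameters is a named safety outcome (SAP 3.3.2). Protocol Appendix 3, section 9, relates the sample size to the precision of toxicity rates, and SAP 3.2 says that the estimates will be used to plan later trials. Protocol 6.5.1 counts hematologic and non-hematologic reactions of Grade 3 or higher as dose limiting. SAP 11.1.2 already takes the most severe treatment-emergent event per subject; laboratory grades have no matching rule.

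**Working it through.** The documents give no figure for this point, so there is none to reproduce. The check applies the SAP's rules to cases and then counts days.

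**1. The rules side by side.** The grades and days are assumed for illustration.

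| Results after one implant | Tabulated under 6.4.3 (last in window) | Tabulated under 6.1 (repeat excluded) | Subject's worst grade |
|---|---|---|---|
| Day 14 Grade 4, repeat Day 18 Grade 1 | 1 | 4 | 4 |
| Day 14 Grade 1, repeat Day 18 Grade 4 | 4 | 1 | 4 |
| Day 4 Grade 3, Day 14 Grade 1 | 1 | 1 | 3 |

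Each rule misses the worst grade in one of the first two cases. Both miss it in the third.

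**2. How often a repeat shares the window.** Inputs: the protocol allows visits on Day 14 ± 3 and on Days 30, 60 and 90 ± 5 (Protocol 5.1.6-5.1.9). Each SAP window ends 7 days after its target day (SAP 6.4.4). Assumption: every allowed visit day counts equally.

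Number of allowed visit days: 7 + 3 × 11 = 40.

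For a visit with tolerance t and a repeat L days later, the number of visit days that keep the repeat in the window is min(2t + 1, 8 + t − L). Over the four visits this gives

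min(7, 11 − L) + 3 × min(11, 13 − L).

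| Lag L (days) | Day 14 visit | Days 30, 60, 90 | Total of 40 | Share |
|---|---|---|---|---|
| 1-2 | 7 | 3 × 11 = 33 | 40 | 100% |
| 3 | 7 | 3 × 10 = 30 | 37 | 93% |
| 4 | 7 | 3 × 9 = 27 | 34 | 85% |
| 5 | 6 | 3 × 8 = 24 | 30 | 75% |
| 6 | 5 | 3 × 7 = 21 | 26 | 65% |
| 7 | 4 | 3 × 6 = 18 | 22 | 55% |

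Otherwise the repeat falls in a gap between windows or, for 1 visit day at a lag of 6 and 2 at a lag of 7, in the next window. The first value then stays in the table for its own visit.

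**3. Days outside every window.** The four windows cover 4 × 15 = 60 of Days 1-97, which leaves 97 − 60 = 37: Days 1-6 (6), Day 22 (1), Days 38-52 (15) and Days 68-82 (15). A value on any of these days is unscheduled and enters no summary table, whatever its grade. Days 1-6 directly follow surgery, when Protocol 5.1.4 leaves blood sampling to clinical need.

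**The case against.** The strongest reply is that SAP 6.1 names repeat laboratory tests as its example of data to leave out. If 6.1 governs, a recovered repeat is ignored, the Grade 3-4 value stays in the table, and nothing is lost in that case. This stands. A reader might infer from 6.4.3 alone that a Grade 3-4 result followed by recovery always vanishes from the tables. The documents do not support that, because it follows from only one of two conflicting rules and requires the repeat to fall in the same window.

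A reader might also infer a bias towards recovery, on the view that abnormal results prompt repeats. The protocol sets no retest rule; evaluations at unscheduled visits are at the investigator's discretion (Protocol 5.3). A later value in the window may also be worse, and 6.4.3 would then raise the grade.

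The severe values are also reported elsewhere. In-window records are all listed, Grade 3 or higher values have their own listing, and a clinically significant asymptomatic value is an adverse event (Protocol 6.1) that can reach the treatment-emergent tables. This limits the harm but does not remove it: a listing gives no incidence, and the adverse event route depends on a judgment of clinical significance rather than on grade.

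Finally, all analyses are exploratory (SAP 6.2), and the accrual stopping rule uses Grade 5 adverse events (Protocol 6.6), not these tables. Both points are right and bear on priority.

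**Conclusion.** The SAP has an unresolved conflict on in-window repeats and no rule that shows a subject's worst laboratory grade. The toxicity-grade, out-of-range and shift tables can therefore miss transient Grade 3-4 values on either reading. Under 6.4.3 the overlap would be common for prompt repeats (75% or more up to a lag of 5 days, with allowed visit days weighted equally). The 37 uncovered days are lost under both rules.

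It is tempting to turn this into an understated incidence, but the documents give no rate of Grade 3 or higher values, of repeat testing or of recovery. For scale only, assume that 5% of samples at a visit are Grade 3 or higher, that 50-80% of these are repeated in the window, and that 50-90% of repeats have recovered. Under 6.4.3 the table for that visit would show between 5% × (1 − 0.8 × 0.9) = 1.4% and 5% × (1 − 0.5 × 0.5) = 3.75%. Under 6.1 it would show the full 5%. This ignores worsening repeats and is not an estimate for this trial.

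The loss is confined to the laboratory summary tables. The point should be fixed, but it does not affect the mortality analysis or the stopping rule.

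**What to change.** 1. In SAP 11.1.3, add toxicity-grade and shift-to-worst tables for the graded parameters. Base them on the worst post-baseline grade per subject, after each implant and overall, using every recorded result, including repeats and values outside the windows.
2. State this as an exception in SAP 6.1, 6.2, 6.4.2 and 6.4.3. Amending only 6.1 and 6.4.3 is not enough, because 6.2 and 6.4.2 would still bar the out-of-window values.
3. State one rule for in-window repeats in the by-visit summaries, so that 6.1 and 6.4.3 agree.
4. Keep the by-visit rule for means, medians and the existing by-time-point tables.

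The new tables can then be checked against Listing 16.2.8.4. The cost is SAP wording and minor programming, with no new data collection. Reported laboratory toxicity may be higher than under the present rules.

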6.4.4 Visit windows definitions

The following visit window definitions will be used:

Implant	Time Window			Comment
	From Day (inclusive)	Assessment Day	To Day (inclusive)	
Pre-implant	-28	< 0	0	Implant 1 Baseline
1	---	0	---	Implant 1 Day 0
	7	14	21	Implant 1 Day 14 (I1 / D14)
	23	30	37	Implant 1 Day 30 (I1 / D30)
	53	60	67	Implant 1 Day 60 (I1 / D60)
	83	90	97	Implant 1 Day 90 (I1 / D90) if before Implant 2 or there is no Implant 2
2	---	0	---	≥ 98 days after Implant 1, Day 0 Implant 2 Day 0 (I2 / D0)
	7	14	21	Implant 2 Day 14 (I2 / D14)
	23	30	37	Implant 2 Day 30 (I2 / D30)
	53	60	67	Implant 2 Day 60 (I2 / D60)
	83	90	97	Implant 2 Day 90 (I2 / D90) if before Implant 3 or there is no Implant 3
3	---	0	---	≥ 98 days after Implant 2, Day 0 Implant 3 Day 0 (I3 / D0)
	7	14	21	Implant 3 Day 14 (I3 / D14)
	23	30	37	Implant 3 Day 30 (I3 / D30)
	53	60	67	Implant 3 Day 60 (I3 / D60)
	83	90	97	Implant 3 Day 90 (I3 / D90) if before Implant 4 or there is no Implant 4
4	---	0	---	≥ 98 days after Implant 3, Day 0 Implant 4 Day 0 (I4 / D0)
	7	14	21	Implant 4 Day 14 (I4 / D14)
	23	30	37	Implant 4 Day 30 (I4 / D30)
	53	60	67	Implant 4 Day 60 (I4 / D60)
	83	90	97	Implant 4 Day 90 (I4 / D90)

Implant	Time Window			Comment
	From Day (inclusive)	Assessment Day	To Day (inclusive)	
	113	120	127	EOS
Any visit which occurs outside the above time windows is considered "unscheduled".				

7 BASELINE CHARACTERISTICS

7.1 Demographics

Demographics (age, sex, and race / ethnicity) at Screening will be recorded in the CRF and will be included in the Baseline Characteristics listing and summary table. Age will be calculated by subtracting the date of birth from the Screening date, dividing by 365.25, and rounding down to the nearest integer.

7.2 Other Baseline Characteristics

A listing of satisfaction of each inclusion / exclusion criteria recorded in the CRF will be provided. A separate Subject Eligibility listing will include whether or not all inclusion / exclusion criteria were met, waivers granted (if any), confirmation that eligibility was evaluated and study procedures were understood, and ICF signature and approval dates. These data will be recorded in the CRF.

Medical history at Screening will be recorded in the CRF. Each subject's medical history including condition, onset date, end date, and whether or not the condition is ongoing will be listed.

Disease history, including cancer type, date and method of first diagnosis, treatment history and current status will be recorded in the CRF. For current diagnosis, locations of metastases and time from diagnosis to first implantation will be summarized; for previous diagnosis, tumor location will be summarized.

Contraceptive methods will be ascertained at Screening and will be recorded in the CRF. For women, childbearing potential and contraceptive methods or reason for non-childbearing potential will be listed and summarized; for men, vasectomy status and contraceptive methods will be listed and summarized.

Height and weight at Screening will be recorded in the CRF and will be included in the Baseline Characteristics listing and summary table.

8 MACROBEAD IMPLANTATION

Details of macrobead implantations will be recorded in the CRF. For each implantation, date, start and end time of the implantation procedure, the number of beads implanted with associated lot numbers, subject vital signs, anesthesia and cefazolin status will be listed. The total number of implantations, and the number of macrobeads implanted per implantation, will be summarized.

9 MEDICATION USE

Prescription, over-the-counter, and alternative medication use within 30 days of implantation and through the EOS visit will be recorded in the CRF and will be coded to generic terms using the World Health Organization Drug Dictionary (WHO^{DD}) version 2008Q1 (March 2008) or later, B2 format. Coding will be done by DM using a computer algorithm for exact matches or manual coding for incomplete or non-matches. All coding will be reviewed by a second member of the DM team. The Medical Monitor will review and approve the final coding prior to database lock.

Separate listings will be done for pre-implantation and concomitant medications and will include WHO^{DD} drug class, WHO^{DD} preferred drug name, reported drug name, start and stop date, study day in relationship to both first and most recent implantation, dose, route, regimen and indication. Concomitant medication use will be summarized by numbers and percentages of subjects reporting each preferred name and also by WHO^{DD} drug class and preferred name within drug class. Medications that were stopped within a 7-day window prior to implantation will be considered “pre-implantation.” All other medications will be considered concomitant. If medication exposure dates cannot be determined due to missing or partially missing start and/or stop dates, the medication will be considered concomitant.

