15. The subject has provided signed informed consent.

4.3.2 Exclusion Criteria:

1. Any condition (cardiovascular or other), making subject an unacceptably high anesthetic or surgical risk based on current anesthesia/general surgery standards.
2. Positive testing for HIV.
3. Cognitive impairment sufficient to render the subject incapable of giving informed consent.
4. Hypersensitivity reaction that, in the opinion of the investigators, poses an increased risk of an allergy to the macrobeads, particularly any known allergy to murine antigens or body tissues.
5. Surgical treatment or chemotherapy within three weeks of scheduled macrobead implantation or within four weeks of bevacizumab (or similar drugs), or radiation therapy within four weeks of scheduled macrobead implantation.
6. Investigational medications for their respective tumors within one month of baseline evaluation.
7. The subject has inadequate hematologic function (absolute neutrophil count [ANC] <1500/mL, hemoglobin <9 g/dL, and platelets <100,000/mL).
8. The subject has inadequate hepatic function [bilirubin >1.5 times the upper limit of normal (ULN)], aspartate transaminase [AST] and alanine transaminase [ALT] > 3 times the ULN, or > 5 times the ULN, if liver metastases are present).
9. The subject has inadequate renal function (serum creatinine > 2.0 mg/dL).
10. The subject has inadequate coagulation function (an international normalized ratio [INR] > 1.5 and a partial thromboplastin time [PTT] > 5 seconds above the ULN [unless on oral anticoagulant therapy]). Subjects receiving full-dose anticoagulation therapy are eligible provided they meet all other criteria, are on a stable dose of oral anticoagulant or low molecular weight heparin (and if on warfarin have a therapeutic INR between 2 and 3).
11. Hepatic blood flow abnormalities: portal vein hypertension and thrombosis; and/or large volume of ascites.
12. Concurrent cancer of any other type except skin cancer (excluding melanoma).
13. History of allergic reactions to mouse antigen.
14. The subject has an ongoing or active infection, symptomatic congestive heart failure, unstable angina pectoris, serious cardiac arrhythmias, (well-controlled atrial fibrillation, is permitted,) psychiatric illness/social situations that could interfere with the subject's ability to participate in the protocol, active bleeding.

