10.1.4.1	Global Clinical Assessment (GCA).....	24
10.1.4.2	Activities of daily living (ADL) rating / Karnofsky performance status scale	24
10.1.4.3	Quality of life scale / EORTC QLQ-C30	24
10.1.4.4	Pain scale	24
10.1.4.5	Eastern Cooperative Oncology Group (ECOG) performance status	24
10.2	Statistical Analysis Methods	25
11	SAFETY ANALYSES.....	25
11.1	Safety Outcomes	25
11.1.1	Subject disposition	25
11.1.2	AEs.....	26
11.1.3	Clinical laboratory evaluations	27
11.1.4	Vital signs and weight	27
11.1.5	12-Lead electrocardiogram (ECG).....	28
11.1.6	Physical examination	28
11.1.7	Murine antigens skin test	28
11.1.8	Murine leukemia virus	28
12	MISCELLANEOUS DATA COLLECTION.....	28
12.1	Subject Progress	28
13	STATEMENT OF COMPLIANCE	28
14	SOFTWARE	28

15 REFERENCES	29
16 APPENDICES	30
16.1 Listings	30
16.2 Tables	32
16.3 Figures	34

List of Abbreviations

ADL	Activities of daily living
AE	Adverse event
ALT	Alanine aminotransferase
AST	Aspartate aminotransferase
BUN	Blood urea nitrogen
CA	Cancer antigen
CEA	Carcinoembryonic antigen
CI	Confidence interval
CRA	Clinical Research Associate
CRF	Case report form
CSR	Clinical study report
CT	Computerized tomography
CTCAE	Common terminology criteria for adverse events
DM	Data management
ECG	Electrocardiogram
ECOG	Eastern Cooperative Oncology Group
EORTC	European Organisation for Research and Treatment in Cancer
EOS	End of study
ESR	Erythrocyte sedimentation rate
GCA	Global clinical assessment
GGT	Gamma glutamyl-transpeptidase
ICF	Informed consent form
Ig	Immunoglobulin
IL	Interleukin
INR	International normalized ratio
KPS	Karnofsky Performance Status
LLT	Lowest level term
MedDRA®	Medical Dictionary for Regulatory Activities
MRI	Magnetic resonance imaging
NK	Natural killer
PA	Posteroanterior
PCR	Polymerase chain reaction
PET-CT	Positron emission tomography - computed tomography

PFS	Progression-free survival
PI	Principal Investigator
PT	Preferred term
PT	Prothrombin time
PTT	Partial thromboplastin time
QLQ-C30	Quality of life questionnaire - C30
RENCA	Renal adenocarcinoma
SAS®	Statistical Analysis System
SAP	Statistical analysis plan
SOC	System organ class
TEAE	Treatment-emergent adverse event
TNF	Tumor necrosis factor
T ₀	Time of origin
VAS	Visual analog scale
VSI	Vital Systems, Inc.
WHO [®] DD	World Health Organization drug dictionary

List of Definitions

Concomitant Medication	Medication taken up to \leq 30 days before the first implantation up to 90 days after the last implantation

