16.2 Tables

Table #	Tables
14.1.1.1	Completion / withdrawal
14.1.1.2.1	Subject disposition, 1 implant
14.1.1.2.2	Subject disposition, 2 implants
14.1.1.2.3	Subject disposition, 3 implants
14.1.1.2.4	Subject disposition, 4 implants
14.1.2.1	Baseline characteristics
14.1.2.2	Contraception methods
14.1.2.3.1	Presenting oncology diagnosis
14.1.2.3.2	Previous oncology diagnosis
14.1.3	Con meds by drug class and preferred name
14.1.4	Number of Implantations and number of macrobeads implanted
14.2.1.1	Global Clinical Assessment
14.2.1.2	Activities of Daily Living
14.2.1.3	Quality of Life Scale (imputed)
14.2.1.3X	Quality of Life Scale (not imputed)
14.2.1.4.1	Pain Scale Assessment, Pain Level
14.2.1.4.2	Pain Location
14.2.1.5	ECOG
14.2.2.1	Tumor markers
14.2.2.2	Cytokines
14.2.3	Tumor size and state
14.2.4	Overall survival (from the most recent radiological scan showing evident disease progression to death)
14.2.5	Time from first implantation to death
14.2.6	Time from diagnosis of Stage IV disease to death
14.3.1.1.1	AE summary
14.3.1.1.2	Death summary
14.3.1.2	Treatment-emergent AEs by SOC
14.3.1.3.1	Treatment-emergent AEs by SOC and preferred term
14.3.1.3.2	Treatment-emergent AEs by severity
14.3.1.3.3	Treatment-emergent AEs by relationship
14.3.1.6	Treatment-emergent frequently reported ($\geq 2\%$ in all patients combined) AEs
14.3.2	Treatment-emergent SAEs by severity
14.3.4.1.1	Serum Chemistry Observed & Changes

Table #	Tables
14.3.4.1.2	Serum Chemistry, out of range flags
14.3.4.1.3	Serum Chemistry, Shift Table
14.3.4.1.4	Serum Chemistry Toxicity Grades
14.3.4.2.1	Hematology Observed & Changes
14.3.4.2.2	Hematology, out of range flag
14.3.4.2.3	Hematology, Shift Table
14.3.4.2.4	Hematology Toxicity Grades
14.3.5.1	Physical exam
14.3.6.1	Vital signs
14.3.6.2	Vital signs from diary
14.3.7	ECG

Mortality Figures	
16.2.6.4.1	Overall survival (from the most recent radiological scan showing progression)
16.2.6.5.1.1	Time from first implantation to death
16.2.6.5.1.2	Time from diagnosis of Stage IV disease to death

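### SAP Section 9 counts drugs stopped 8 to 30 days before implantation as concomitant but not those stopped in the last 7 days, and the SAP's own definition contradicts it

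*SAP*

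**What the plan says.** SAP Section 9 states that "medication use within 30 days of implantation and through the EOS visit will be recorded in the CRF". It then divides the recorded drugs. "Medications that were stopped within a 7-day window prior to implantation will be considered" pre-implantation, and "All other medications will be considered concomitant". Both classes are listed by subject with start and stop dates, but only one is summarized: "Concomitant medication use will be summarized by numbers and percentages of subjects reporting each preferred name", and also by drug class. The matching output in SAP 16.2 is Table 14.1.3, "Con meds by drug class and preferred name".

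The SAP List of Definitions has a different rule. Concomitant medication there begins 30 days before the first implantation and runs "up to 90 days after the last implantation", with no exception for the last 7 days. Protocol 5.1.1 also places drugs taken in the 30 days before implantation under the concomitant medication assessment.

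Exclusion criterion 5 in Protocol 4.3.2 rules out "Surgical treatment or chemotherapy within three weeks of scheduled macrobead implantation", and sets four weeks for bevacizumab or similar drugs. Protocol 5.9 allows rescue therapy, including chemotherapy, without removing the subject from the protocol. Treatment-emergent adverse events are counted to 120 days after the last implant (SAP List of Definitions and 11.1.2).

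**The concern.** A pre-implantation class should hold drugs whose use had ended before the macrobeads went in. Section 9 puts only the most recently stopped drugs there and sends those stopped earlier to the concomitant class. The order is reversed: the longer a drug has been stopped, within the 30 days recorded, the more surely it is called concomitant.

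The washout makes this matter for anticancer drugs in particular. Chemotherapy that complies with the protocol cannot have stopped in the last 7 days before the first implant, so it can never be labelled pre-implantation. In the one summary table of medications, a subject whose chemotherapy ended before the first implant looks the same as a subject given rescue chemotherapy on study. In a single-arm trial that permits rescue, and whose survival methods (SAP 10.1.1 and 10.2) do not mention it, the count of subjects who received other anticancer drugs after implantation is one that readers will look for.

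**Working it through.** The plan states no figure on this point, so there is none to reproduce. The check is to apply each rule to every possible stop day.

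**Inputs**
- Recording window: 30 days before implantation to the end-of-study (EOS) visit (SAP 9).
- Section 9 split: stopped within 7 days before implantation, against all others.
- Definitions split: anything taken from 30 days before the first implant to 90 days after the last.
- Washout: three weeks for chemotherapy, four weeks for bevacizumab or similar drugs (Protocol 4.3.2).
- EOS visit: 120 days after the last implant (SAP 6.4.1.10).

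**Start of the period.** Let d be the number of days from stopping the drug to the first implant, d = 1 to 30.
- Section 9: pre-implantation for d = 1 to 7, which is 7 days; concomitant for d = 8 to 30, which is 30 − 8 + 1 = 23 days.
- Permitted chemotherapy in the window: d = 21 to 30, which is 30 − 21 + 1 = 10 days. If exactly 21 days counts as inside the washout, d = 22 to 30, which is 9 days.
- Permitted bevacizumab-type drugs: d = 28 to 30 (3 days) or d = 29 to 30 (2 days).
- None of these washout-compliant days overlaps d = 1 to 7.

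| Rule | Stop days called concomitant, of 30 | Permitted chemotherapy stop days called concomitant |
|---|---|---|
| Section 9 as written | 23 | all 9 or 10 |
| List of Definitions | 30 | all 9 or 10 |
| Mirror of Section 9 (stopped more than 7 days before = pre-implantation) | 7 | 0 |
| Stopped before the first implant = pre-implantation | 0 | 0 |

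The two SAP rules disagree for d = 1 to 7, and neither separates finished chemotherapy from on-study treatment.

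**End of the period.** Section 9 runs to 120 days and the Definitions to 90, a difference of 120 − 90 = 30 days (Days 91 to 120). Under the Definitions, a drug begun in those days is not concomitant, although an adverse event on the same day is treatment-emergent.

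**Anchor.** The Definitions refer to the first implantation. Section 9 says only implantation, and there can be four. If the 7 days apply to each implant, a drug taken after implant 1 and stopped 3 days before implant 2 could be labelled pre-implantation and leave the table, although it was used on study. Rescue chemotherapy would not be caught this way if the three-week break in Protocol 5.9 is kept; other drugs could be.

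**The case against.** The strongest reply is that little depends on the label. Section 9 lists every drug with its start and stop dates and its study day relative to both the first and the most recent implant, and the adverse event listings use the same two anchors (SAP 11.1.2). A drug stopped on Day -25 can be recognised as such under either label. The mortality analyses and adverse event summaries do not use the classification, and all analyses are exploratory. This stands, and it limits the point to descriptive medication outputs.

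A second reply is that the 30-day look-back is a convention: the List of Definitions and Protocol 5.1.1 both place it under concomitant. This stands in part. It means that calling earlier chemotherapy concomitant is not peculiar to Section 9. It does not explain why Section 9 removes the last 7 days, and it leaves the SAP with two incompatible rules.

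Three stronger readings are tempting, and the documents do not support them.
- A reader might infer that adverse events and responses cannot be related to other treatment. They cannot be from Table 14.1.3 alone, but the dated listings allow it.
- A reader might infer that rescue begun on Days 91 to 120 is dropped. That follows only from the Definitions. Section 9 records to the EOS visit and classes it as concomitant.
- A reader might infer that all prior chemotherapy is miscounted. Chemotherapy that ended more than 30 days before the first implant is outside this window; SAP 7.2 captures treatment history separately.

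One might also suppose that Section 9 meant its mirror image, with drugs stopped more than 7 days before being pre-implantation. The sentence assigning all others to the concomitant class does not allow that reading.

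**Conclusion.** The rule is wrong as written and contradicted within the SAP. Section 9 sends 23 of 30 pre-implant stop days, including every washout-compliant chemotherapy stop day in the window (9 or 10), into the same table as on-study rescue. The List of Definitions disagrees with it on the last 7 days before implantation and, by 30 days, on the end of the period. The anchoring implant is not named in Section 9.

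These are counts of days, not of subjects. The documents do not show how many subjects stopped chemotherapy in that band; it could be none. The conclusion assumes that anticancer drugs are entered on the medication pages as prescription drugs, since Section 9 does not exclude them, and that subjects met the washout. The harm is a misleading descriptive table and an unresolved contradiction. Survival estimates and adverse event counts are not affected. It should be corrected before the tables are produced.

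**What to change.** Put one rule in both SAP Section 9 and the List of Definitions:
- **Pre-implantation:** stop date before the date of the first implant.
- **Concomitant:** ongoing at the first implant, or started on or after it, through 120 days after the last implant, matching the treatment-emergent adverse event period.

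Delete the 7-day sentence and the 90-day limit. Naming the first implant also settles the anchor. The existing rule that undeterminable dates default to concomitant can stay.

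The drug-class summary already planned can carry the rest: within it, show anticancer drugs used on study separately from those stopped before the first implant.

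The cost is one amended rule, one amended definition and a small change to the layout of Table 14.1.3. Start and stop dates are already collected through the EOS visit, so no new data are needed.
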